Interventional Study, open-label, randomized controlled trial.

6. Methodology

- Eligibility

Participant inclusion criteria:

- Patients ≥ 18 years with common bile duct stones are diagnosed by abdominal ultrasound, endoscopic ultrasound, CT scan, or abdominal MRI.
 - No signs of cholangitis at the time of admission, defined by the following criteria:
 - + Non fever (temperature $< 37^{\circ}$ C)
 - + White blood cell count between 4 G/L and 10 G/L
 - Good general condition, classified as ASA Physical Status I or II

Participant exclusion criteria:

• Patients with severe coagulopathy (INR > 1.5 or platelet count < 50 G/L)

Patients with severe systemic illnesses, such as unstable myocardial infarction, respiratory failure, or circulatory failure

- Patients with duodenal perforation or failed ERCP due to inability to access the papilla
- Patients with active infections in other organ systems requiring antibiotic therapy
- Patients have received any systemic antibiotics within 48 hours prior to the ERCP procedure
 - Patients are allergic to antibiotics used in the study.

- Interventions

Patients with common bile duct stones without signs of cholangitis at the time of hospital admission. Patients have an indication for ERCP stone extraction and randomly assigned to one of three study groups by using a simple randomization method in which the remainder of their record number divided by 3 determined the group allocation.

- •Control Group: No Antibiotics Group (Group 1)
- + Medication: normal saline
- + Administration: No antibiotics administered. Patients will receive an intravenous infusion of normal saline on the day of the procedure.
 - •Prophylactic Antibiotic Group (Group 2)
 - + Medication: Amikacin
- + Administration: Amikacin at a dose of 15 mg/kg, diluted in 0.9% NaCl to a total volume of 100mL, administered via intravenous infusion over 60 minutes

+ Timing: Administered 60 minutes before ERCP procedure. For patients with renal impairment,

the Amikacin dose will be adjusted based on glomerular filtration rate (GFR).

- + Other Names: Antibiotic prophylaxis
- •Full-dose Antibiotic Group (Group 3)
- + Medication: Amikacin + Third-generation Cephalosporine
- + Administration: Amikacin at 15 mg/kg/day in combination with Cefoperazone 2 g twice daily, administered by slow intravenous injection every 12 hours
- + Timing: From before the ERCP procedure until hospital discharge, typically lasting 4–7 days.

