After undergoing ERCP, patients will be monitored for signs of infectious complications through clinical symptoms and laboratory tests within 24 to 48 hours post-procedure.

Clinical symptoms include: pulse, blood pressure, consciousness, abdominal pain, fever, jaundice, and melena.

Laboratory tests include: complete blood count and blood biochemistry (urea, creatinine, GOT, GPT, GGT, ALP, total bilirubin, direct bilirubin, CRP, procalcitonin, amylase, lipase).

Patients with high fever > 38°C will undergo blood culture and abdominal CT scan if necessary.

Patients with complications will be monitored clinically, undergo laboratory tests, and receive treatment according to guidelines until they are stable and discharged from the hospital.

[figure not shown]
Outcomes

• Primary Outcome:

Infectious Complications post-ERCP: Fever > 38°C occurring within 24 to 48 hours following ERCP. ¹²

- Secondary Outcomes:
- + Cholangitis: worsening right upper quadrant abdominal pain; fever (ear temperature >38.0 °C); evidence of systemic inflammation: either elevated white blood cell count (>10 G/L) or increased C-reactive protein levels (>10 mg/L), or a further rise if already above the upper normal limit (UNL) prior to ERCP; and indicators of hepatobiliary dysfunction—such as jaundice (total bilirubin >2.0 mg/dL, or worsened if pre-existing), or elevated liver enzymes (GGT, ALP, AST, ALT >1.5×UNL, or further increased if already above UNL before the procedure)¹³.
- + Cholecystitis: Diagnosis was made according to the criteria of the Tokyo Guidelines 2018(TG18)¹³.
 - + Inflamatory markers: WBC, CRP, Procalcitonin
 - + Bacteremia: Positive blood culture for bacteria¹⁴
 - Other Outcomes:
- + Bleeding: Bleeding observed during the procedure or clinical signs such as melena, anemia, and a decrease in hemoglobin level exceeding 2 g/dL^{15} .
 - + Pancreatitis: Diagnosis based on the Revised Atlanta Classification (2012)¹⁶

- Study flowchart

3. Safety considerations

Patients who show signs of infection after undergoing ERCP will be treated with antibiotics according to the Tokyo Guidelines 2018 and the recommendations of the Vietnamese Ministry of Health until they are stable and discharged from the hospital.

Patients who develop other complications such as acute pancreatitis or gastrointestinal bleeding will be treated according to the respective protocols for acute pancreatitis and gastrointestinal bleeding until they are stable and discharged.

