Categorical variables (e.g., rate of cholangitis, mortality rate, etc.) will be compared among the three groups using the Chi-square test. If expected cell counts are small, Fisher's exact test will be used.

Continuous variables (e.g., length of hospital stay, biochemical indices, etc.) will be compared using one-way ANOVA if the data are normally distributed, or the Kruskal-Wallis test if not.

If statistically significant differences are found among the three groups, post-hoc analyses will be conducted to determine which group pairs differ. Differences between groups will be assessed using Relative Risk (RR) along with a 95% Confidence Interval (95% CI). A p-value of less than 0.05 will be considered statistically significant.

• Sample Size Calculation

The sample size was calculated using G*Power software (version 3.1), applying a Chisquare test (goodness-of-fit test) with the following parameters: significance level (α) = 0.05, power (1 – β) = 0.80, and a medium effect size (w = 0.3) as recommended by Cohen¹⁷. This yields a total sample size of 108 participants (36 per group) for a chi-square goodness-of-fit test with 2 degrees of freedom.

6. Quality assurance

The study will be conducted in accordance with ethical regulations for biomedical research involving human participants and has been approved by the Institutional Ethics Committee.

To ensure quality and consistency throughout the implementation process, the research team has developed standard procedures for all steps, including patient selection, intervention, data collection, and data processing.

Monitoring of adverse events, as well as ensuring the integrity and safety of participants, will be jointly conducted by the research team members, the principal investigator, and the hospital's Ethics Committee.

7. Expected outcomes of the study

The study is expected to provide scientific evidence on the effectiveness of prophylactic antibiotic use in preventing post-ERCP infections in patients with common bile duct stones. This may contribute to improving clinical practice guidelines, optimizing antibiotic use, and reducing the risk of antibiotic overuse and resistance

8. Dissemination of results and publication policy

Results will be submitted to peer-reviewed journals and presented at scientific meetings. Participants will be informed of the study outcomes upon request

9. Duration of the Project

The study is expected to be conducted from December 2022 to December 2025

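### The continuous markers are to be compared without their baseline values, although the trial has these for WBC and, by implication, for CRP; precision is lost and no suitable effect measure is named

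*Protocol*

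**What the plan says.** Under Comparison between groups (Data management and statistical analysis), the protocol states that continuous variables such as length of stay and "biochemical indices, etc.) will be compared using one-way ANOVA if the data are normally distributed, or the Kruskal-Wallis test if not". Post-hoc comparisons follow only if the three-group test is significant. The effect measure given is the relative risk with its 95% confidence interval. No covariate, change score or adjusted model appears anywhere in the protocol.

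The Outcomes section lists as a secondary outcome "Inflamatory markers: WBC, CRP, Procalcitonin", with no time point and no statement whether the raw value or a change is meant. The only timing comes from the monitoring text in the Methodology section, which places "laboratory tests within 24 to 48 hours post-procedure".

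What the protocol says about values before ERCP differs by marker:

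- **WBC.** Eligibility requires "White blood cell count between 4 G/L and 10 G/L" at admission, so every participant has a value.
- **CRP.** The cholangitis definition counts "increased C-reactive protein levels (>10 mg/L), or a further rise if already above the upper normal limit (UNL) prior to ERCP". A further rise cannot be judged without a pre-ERCP value.
- **Procalcitonin.** It appears in the post-procedure list ("total bilirubin, direct bilirubin, CRP, procalcitonin, amylase, lipase"), in the follow-up list and as an outcome. No pre-ERCP measurement is described.

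**The concern.** A marker measured 24-48 h after ERCP reflects the patient's starting level as well as any effect of the antibiotics. If the starting level is left out, that part of the variation counts as noise, and any chance difference in baseline between arms stays in the comparison. CRP is the clearer case: eligibility sets no CRP limit, and the cholangitis definition expects that some patients will enter with a raised value.

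There is a second weakness, in estimation. A relative risk does not apply to WBC or CRP analysed as continuous variables. The Kruskal-Wallis branch yields a p-value without an estimate, and a check on the outcome data decides which branch is used. As written, the reader may get no effect size with a confidence interval for these markers.

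**Working it through.** **The plan's own figure.** The sample size section gives 108 participants (36 per group) for a chi-square test with w = 0.3, 2 degrees of freedom, and "significance level (α) = 0.05, power (1 – β) = 0.80". The noncentrality needed for 80% power is 9.635, so N = 9.635 / 0.3² = 107.05, rounded up to 108 (power 0.804). The figure reproduces, but it was set for a chi-square test and says nothing about precision for the markers.

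**Inputs for the check.** From the protocol: n = 36 per arm and two-sided alpha 0.05. Assumed, because the protocol gives neither: a baseline to follow-up correlation r between 0.2 and 0.7, and, for illustration, a true difference of 0.5 SD.

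**Formulas.**

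- Residual variance after adjustment, relative to no adjustment: 1 − r².
- Equivalent unadjusted total sample: 108 / (1 − r²).
- Standard error of a pairwise difference, in SD units: √(2/36) × √(1 − r²) = 0.2357 × √(1 − r²).
- Difference detectable with 80% power: (1.960 + 0.842) × that standard error.
- Power for 0.5 SD: Φ(0.5 / standard error − 1.960).

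| r | 1 − r² | Variance saved | Equivalent total N | Detectable difference (SD) | Power for 0.5 SD |
|---|---|---|---|---|---|
| unadjusted | 1.00 | – | 108 | 0.66 | 0.56 |
| 0.2 | 0.96 | 4% | 113 | 0.65 | 0.58 |
| 0.3 | 0.91 | 9% | 119 | 0.63 | 0.60 |
| 0.5 | 0.75 | 25% | 144 | 0.57 | 0.69 |
| 0.7 | 0.51 | 49% | 212 | 0.47 | 0.84 |

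In terms of patients, 1/0.96 = 1.04 and 1/0.51 = 1.96, that is, about 4% to 96% more.

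**Simulation of the three-arm tests.** Each scenario used 4,000 simulated trials with normal data. With both antibiotic arms 0.5 SD below control, power was about 0.55-0.57 for ANOVA and 0.53-0.55 for Kruskal-Wallis. For ANCOVA it was 0.59, 0.69 and 0.86 at r = 0.3, 0.5 and 0.7. With no effect, all three tests rejected in about 5% of runs.

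**Chance imbalance.** The SD of the baseline difference between two arms of 36 is √(2/36) = 0.24 SD, so differences up to 1.96 × 0.2357 = 0.46 SD are unremarkable. At an assumed r of 0.5, an imbalance of that size shifts the unadjusted contrast by 0.5 × 0.46 = 0.23 SD.

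**The case against.** **This belongs in a SAP, and change scores would fit the wording.** The sentence on continuous variables is generic, the form of the marker outcome is undefined, and ANOVA on change from baseline would be compatible with it. That is fair as far as it goes. However, the protocol does name the test, and it states no change score. A change score would also not be the better choice: its variance relative to the unadjusted value is 2(1 − r), assuming equal variances before and after. This is 1.4 at r = 0.3 and 1.0 at r = 0.5, so it gains nothing until r exceeds 0.5. Since 1 − r² = (1 − r)(1 + r) never exceeds 2(1 − r), ANCOVA is at least as efficient throughout.

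**The gain may be small.** This stands. The correlation is not documented. WBC is restricted to 4-10 G/L at entry, which tends to lower its correlation with the later value. The count is also taken at admission, and patients may wait for ERCP. At r = 0.2 to 0.3, power for 0.5 SD rises only from 0.56 to 0.58-0.60.

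**A conventional choice of test is not an error.** This also stands in part. Choosing between ANOVA and Kruskal-Wallis by a normality check is common, no inflation of error from it has been shown here, and medians with interquartile ranges are planned as descriptive output. None of that supplies a between-group estimate with a confidence interval.

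**A reader might infer that all three markers have an unused baseline.** The protocol does not support this for procalcitonin. The study flowchart is not reproduced in the text at hand, so a baseline sample can be neither confirmed nor excluded.

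**Conclusion.** The point holds for WBC and CRP as a loss of precision and of usable estimates in a secondary outcome. Its size depends on a correlation that the protocol does not give: a 4% to 49% reduction in residual variance over r = 0.2 to 0.7. WBC probably lies near the low end. The upper figure needs r = 0.7, for which the protocol offers no support.

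Two stronger readings should be resisted. The first is that the planned tests are invalid. With sound randomisation they keep their 5% error rate, as the simulation shows. The second is that adjustment would repair the allocation method. Group is set by the remainder of the record number divided by three in an open-label trial, so the assignment is predictable. Adjusting a marker for its own baseline removes only the part of any selection carried by that measured value. Allocation is a separate problem. The primary outcome, fever above 38 °C, is not touched by this point.

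**What to change.** Replace the sentence on continuous variables, as far as it covers the markers, with the following:

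- Analyse 24-48 h WBC and log CRP by ANCOVA, with arm and the pre-ERCP value on the same scale as covariate. State which pre-ERCP sample is the baseline; for WBC this is at least the admission count.
- Report adjusted mean differences (WBC) and geometric mean ratios (CRP) with 95% CI for Group 2 vs Group 1 and Group 3 vs Group 1, whether or not the three-group test is significant.
- Drop the normality check as the rule for choosing the main analysis, and keep Kruskal-Wallis as a sensitivity analysis.
- Apply the same model to log procalcitonin only if a pre-ERCP sample is already taken. Otherwise compare log procalcitonin unadjusted, with 95% CI.

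For WBC and CRP the cost is analysis wording only: no extra patients or visits, no new sample provided the pre-ERCP CRP implied by the cholangitis definition is recorded, and the model is available in SPSS 22. Adjusting procalcitonin would cost an added blood test if no baseline sample exists, and the fix does not depend on it.

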Endoscopic Retrograde Cholangiopancreatography (ERCP) is an important method for diagnosing and treating biliary and pancreatic diseases, among which common bile duct stones are one of the most frequently encountered causes. However, ERCP is an invasive procedure with a high risk of complications, including acute pancreatitis, bleeding, hollow organ perforation, and infection. Among these, infectious complications occur in approximately 5% to 18% of cases and account for around 10% of ERCP-related mortality¹⁻³.

To minimize the risk of infection, several strategies have been proposed, such as limiting the injection of contrast into the bile duct, aspirating bile to reduce biliary pressure, ensuring complete biliary drainage, and using prophylactic antibiotics⁴. However, the clinical effectiveness of prophylactic antibiotic use remains controversial. A meta-analysis by Cochrane et al. (2010) showed that prophylactic antibiotics can reduce the risk of bacteremia and cholangitis⁵. In contrast, a more recent meta-analysis by Maria Fernanda Shinin Merchan (2022), along with several other studies, suggested that prophylactic antibiotics may reduce

the rate of bacteremia but do not significantly decrease the incidence of cholangitis, sepsis, post-ERCP pancreatitis, or mortality⁶⁻⁸.

Rational antibiotic use remains a significant challenge for clinicians, as broad-spectrum antibiotic treatment can lead to unnecessary costs and contribute to the growing problem of antibiotic resistance—a serious global health concern causing approximately 700,000 deaths annually and an estimated economic burden ranging from 1 to 3.4 trillion USD. This figure continues to rise⁹⁻¹¹.

According to guidelines from major organizations such as the American Society for Gastrointestinal Endoscopy (ASGE) and the European Society of Gastrointestinal Endoscopy (ESGE), routine prophylactic antibiotic use is not recommended, except in cases of incomplete biliary drainage or in immunocompromised patients. However, these recommendations are based on low-quality evidence and remain weak in strength.

Therefore, we designed this study to evaluate whether prophylactic antibiotic use can reduce infectious complications after ERCP in patients with common bile duct stones.

4. Objectives

To evaluate whether prophylactic antibiotic use can reduce infectious complications after ERCP in patients with common bile duct stones.

5. Study Design

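### The prophylaxis-versus-control comparison that answers the objective is not named as primary and is tested only if the three-group test is significant

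*Protocol*

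**What the plan says.** The Project Summary and the Objectives section give one aim: "to evaluate whether prophylactic antibiotic use can reduce infectious complications after ERCP in patients with common bile duct stones". The Interventions section defines a no-antibiotic control (Group 1), a prophylactic arm given amikacin before ERCP (Group 2) and a full-dose arm treated until discharge (Group 3). The primary outcome is binary: "Infectious Complications post-ERCP: Fever > 38°C occurring within 24 to 48 hours following ERCP".

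Under Comparison between groups, categorical outcomes "will be compared among the three groups using the Chi-square test", with Fisher's exact test when expected counts are small; the cut-off is not given. Pairs come next, conditionally: "If statistically significant differences are found among the three groups, post-hoc analyses will be conducted to determine which group pairs differ". The following sentence reads "Differences between groups will be assessed using Relative Risk (RR) along with a 95% Confidence Interval (95% CI". It names no pair and does not say whether it applies when the three-group test is not significant. The significance level is 0.05. The sample size, 108 in total and 36 per group, is for a chi-square test with 2 degrees of freedom and w = 0.3.

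**The concern.** The three-group test asks whether any of three rates differ. The objective asks whether one particular rate is lower than another. The two can part company in both directions.

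- **Significant overall test.** It may reflect Group 3 alone and say nothing about prophylaxis.
- **Non-significant overall test.** The plan as written stops, and its own question is never tested, even where the direct comparison would have been significant.

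At the same level, the gated rule rejects only in a subset of the outcomes in which the direct test rejects. It can therefore only lose power for the objective. If the effect estimate is also withheld when the gate fails, the estimates that do get reported are a selected set and too large on average. The gate is written into the protocol, so this is not a detail left to a statistical analysis plan.

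**Working it through.** **The plan's own figure.** For a 2-df chi-square test with non-centrality N × w²:

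- N = 108: 108 × 0.09 = 9.72, power 80.37%
- N = 107: 107 × 0.09 = 9.63, power 79.98%

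The stated 108 reproduces. It is the power of the three-group test at w = 0.3, not of Group 2 versus Group 1.

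**Inputs.** From the protocol: 36 per arm, level 0.05, the three-group test first, and Fisher's test when expected counts are small. Assumed: Fisher's test applies when any expected count is below 5. The protocol gives no arm-specific rates, only an overall 5% to 18% for infectious complications. The rates for Groups 1/2/3 below are therefore assumptions. Most lie in that range; one scenario lies partly above it.

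**Method.** All 37³ = 50,653 possible outcomes (x₁, x₂, x₃) were enumerated, each weighted by the product of Bin(xᵢ; 36, pᵢ).

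- Direct power = total weight of outcomes where the Group 1–2 test is significant.
- Gated power = total weight of outcomes where both the three-group test and the Group 1–2 test are significant.

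**How often Fisher's test applies.** The mean expected event count per arm is 36 × average rate:

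- 18/5/12%: 36 × 0.35/3 = 4.2
- 18/5/5%: 36 × 0.28/3 = 3.4
- 18/9/9%: 36 × 0.36/3 = 4.3

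The three-group table would fall under Fisher's test in about 73%, 93% and 69% of trials respectively.

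**Power for Group 2 versus Group 1**

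| Assumed rates, Groups 1/2/3 | Direct, Fisher switch | Gated, Fisher switch | Loss | Direct → gated, Pearson throughout | Direct → gated, Fisher throughout |
|---|---|---|---|---|---|
| 18/5/12% | 30.4% | 25.1% | 5.3 | 44.5% → 28.9% | 25.8% → 23.7% |
| 18/5/5% | 30.4% | 27.9% | 2.5 | 44.5% → 36.6% | 25.8% → 25.1% |
| 18/9/9% | 15.8% | 12.3% | 3.5 | 20.8% → 14.5% | 11.3% → 10.1% |
| 30/10/20% | 57.0% | 44.6% | 12.4 | 57.9% → 45.1% | 47.2% → 41.1% |

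**How often the gate opens.** With the Fisher switch, the three-group test is significant in about 30%, 41% and 19% of trials in the first three scenarios. In the other 59% to 81% (100 − 41 and 100 − 19) no pairwise test follows.

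**Wrong driver.** At 18/18/5%, where prophylaxis does nothing and only full dose works, the three-group test is significant in about 39% of trials.

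**Selected estimates.** This is the mean Group 1 minus Group 2 risk difference among trials with a significant three-group test, with the Fisher switch:

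- 18/5/5%: 19.1 points against a true 18 − 5 = 13
- 18/9/9%: 18.4 points against a true 18 − 9 = 9

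With Pearson throughout the figures are 18.8 and 18.2. Selecting instead on a significant direct Pearson test gives 19.2 and 19.4.

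**The case against.** Several defences carry weight.

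- **Type I error.** With three arms, an overall test followed by pairwise tests is a recognised way to control the error rate. A reader might infer that the gate inflates alpha; it does not. The sample size rests on the same 2-df test, so sizing and first-stage analysis agree with each other. What they do not match is the objective.
- **Size of the power loss.** A reader using Pearson's test alone would find losses of 7.9 points (44.5 − 36.6) and 15.6 points (44.5 − 28.9) at 18% versus 5%. The plan's Fisher rule does not support those as the headline: it would govern most tables at such rates. With Fisher at both stages the loss is only 0.7 to 2.1 points in the first three scenarios. The larger loss holds only at higher event rates.
- **Exaggerated effects.** A reader might infer that the published effect will be inflated. The relative-risk sentence does not expressly depend on the gate, and group frequencies and percentages are to be presented in any case. Selecting on a significant direct test inflates about as much. The cure is to report the estimate always; removing the gate alone would not do it.
- **Trial size.** Low power comes mainly from 36 per arm, not from the gate. A direct test with 80% power needs about 94 per arm at 18% versus 5%, and about 226 at 18% versus 9%.
- **Zero events.** An arm without events makes the relative risk awkward, but interval methods for that case are commonly left to a statistical analysis plan.

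None of this answers the core point: the comparison that the objective calls for is unnamed, and its test is conditional on a different hypothesis.

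**Conclusion.** The point holds as a mismatch between the objective and the testing rule, with a modest cost in power. In the three scenarios within 5% to 18%, the gate costs about 2.5 to 5 points and leaves the objective without a pairwise test in about 59% to 81% of trials. At 30/10/20% it costs about 12 points. These figures assume the listed rates, a Fisher cut-off of 5, and that the objective means Group 2 against Group 1, as the arm labels indicate.

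Inflation of the estimate is conditional: about 19 points against a true 13, or about 18 against a true 9, if results are reported only after a significant three-group test. The text neither states nor excludes that reading. The documents do not support a claim of inflated type I error or of certain exaggeration.

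**What to change.** Amend Comparison between groups as follows:

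1. Name Group 2 versus Group 1 on the primary outcome as the primary comparison, two-sided 0.05, not conditional on the three-group test.
2. State that its relative risk and risk difference, each with a 95% CI, are reported whatever the test results.
3. Make Group 3 versus Group 1 the next comparison, tested at 0.05 only if the first is significant. This fixed sequence controls the error rate across the two tests.
4. Do not present the 80% power of the 2-df test as the power of the primary pairwise comparison.

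This costs wording only: no added patients, visits or data. The downside is that Group 3 comparisons become secondary, and the Group 3 versus Group 1 test loses confirmatory standing if the primary comparison fails. The amendment should be dated before outcomes are examined by group, because choosing the contrast afterwards would itself be driven by the data.

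### The 80% power rests on a generic w = 0.3 with no event rates behind it; at the protocol's own 5–18% infection rates, 36 per group gives under 50%

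*Protocol*

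**What the plan says.** Under Data management and statistical analysis, the Sample Size Calculation gives three inputs: "significance level (α) = 0.05", "power (1 – β) = 0.80" and "a medium effect size (w = 0.3) as recommended by Cohen". It then concludes: "This yields a total sample size of 108 participants (36 per group) for a chi-square goodness-of-fit test with 2 degrees of freedom". It states no control rate, no target reduction and no rate for either antibiotic arm.

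The Comparison between groups paragraph describes the analysis itself. Categorical outcomes "will be compared among the three groups using the Chi-square test. If expected cell counts are small, Fisher's exact test will be used". If that test is significant, "post-hoc analyses will be conducted to determine which group pairs differ", with relative risks and 95% confidence intervals. The primary outcome is binary: fever above 38°C in the stated window after ERCP.

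The only infection rates in the protocol are in the Project Summary and in the Rationale and Background Information, where "infectious complications occur in approximately 5% to 18% of cases". The sample-size paragraph does not use them.

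**The concern.** A goodness-of-fit test asks whether one sample is spread over categories in given proportions. It does not compare event rates between arms, so the paragraph names a test that the trial will not run. More important, w = 0.3 is called medium by a general convention and is never translated into infection rates. For an infrequent binary event in three arms, w depends strongly on the underlying rates, and a value that sounds moderate can require a very large reduction.

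If the rates are near those the protocol cites, the trial would more often than not miss even a fall from 18% to 5%. The Expected outcomes section hopes to inform guidelines and reduce antibiotic overuse. A reader who takes the 80% at face value could then give a non-significant result more weight than it can bear.

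**Working it through.** **Inputs.** Alpha 0.05, power 0.80, w = 0.3, 2 df, N = 108 and 36 per group come from the Sample Size Calculation. The tests come from Comparison between groups. The 5–18% range comes from the Rationale. Applying that range to individual arms is an assumption of this check. Rates below are in the order control / prophylactic / full-dose.

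**Step 1: reproduce the stated N.** With 2 df and alpha 0.05 the critical value is 5.991, and 80% power needs a noncentrality of 9.635. Since noncentrality = N·w², N = 9.635 / 0.3² = 9.635 / 0.09 = 107.05. This rounds up to 108, where power is 80.4%. The figure reproduces. A 3x2 test of independence has (3 − 1)(2 − 1) = 2 df, so w = 0.3 gives 108 under the correct label as well.

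**Step 2: what w is at the cited rates.** For three equal arms, w² = mean[(pᵢ − p̄)²] / [p̄(1 − p̄)].

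- 18/5/5%: p̄ = 0.0933; mean squared deviation = (0.0867² + 2 × 0.0433²)/3 = 0.00376; p̄(1 − p̄) = 0.0846; w² = 0.0444; w = 0.211. Noncentrality = 108 × 0.0444 = 4.79, about half of the 9.635 required.
- 18/9/9%: p̄ = 0.12; w² = 0.0018/0.1056 = 0.0170; w = 0.131.
- By the same formula, 18/9/5% gives w = 0.176 and 10/5/5% gives w = 0.094.

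**Step 3: power with 36 per group.** The exact columns enumerate every outcome of three binomials of size 36. Fisher is the 3x2 (Freeman-Halton) form.

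| Rates (%) | w | Large-sample | Exact Pearson | Exact Fisher |
|---|---|---|---|---|
| 18/5/5 | 0.211 | 48.6% | 45.5% | 40.6% |
| 18/18/5 | 0.178 | 36% | 39% | 38% |
| 18/9/5 | 0.176 | 36% | 34% | 31% |
| 18/9/9 | 0.131 | 21% | 21% | 17.5% |
| 10/5/5 | 0.094 | 13% | 11% | 9% |

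Of the patterns checked with all rates inside 5–18%, 18/5/5% is the most favourable. On the large-sample method it would need 219 patients (73 per group) for 80% power.

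**Step 4: which column applies.** The protocol does not define a small expected count. With the usual threshold of 5 (an assumption), the smallest expected cell is total events / 3, so Fisher applies whenever there are fewer than 15 events in all. At 18/5/5% the expected total is 36 × 0.28 = 10.1 events. Fewer than 15 occur in 93% of trials at 18/5/5% and in 69% at 18/9/9%. The Fisher column is therefore usually the relevant one.

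**Step 5: rates that would give w = 0.3.** Take the two antibiotic arms as equal and solve the formula in step 2.

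- Control 18%: both antibiotic arms must be about 1.65%. Exact power is then 78.0% (Pearson) or 75.0% (Fisher).
- Antibiotic arms 5%: control must be about 25.6%, above the cited 18%. Exact power is then about 79% (Pearson) or 73% (Fisher).
- At 18/2/2% Fisher gives 71%; at 18/1/1% it gives 82%.

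**Step 6: precision.** The 95% half-width for a risk difference is 1.96·√[p₁(1 − p₁)/36 + p₂(1 − p₂)/36]. This gives 14.4 points for 18% vs 5%, 15.6 for 18% vs 9% and 12.1 for 10% vs 5%.

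**The case against.** The strongest reply is that nothing has been miscalculated. The software result is right for its inputs, and the design does have about 80% power for w = 0.3. That stands: the fault is an effect size with no rates behind it.

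The second reply is that 5–18% describes infectious complications after ERCP in general. It is not given by arm, for stone patients without cholangitis, or for this fever endpoint. That also stands. A control rate near 26%, or antibiotic-arm rates near 1%, would bring power close to 80%. But the protocol states and justifies neither, and its Rationale calls the clinical effectiveness of prophylaxis controversial. The power figures must therefore be read as conditional on assumed rates.

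Three stronger readings may tempt a reader, and the document does not support them.

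- That the goodness-of-fit label made the trial too small. It did not; N is 108 under either test.
- That 108 should count infection events. The text says participants and gives 36 per group.
- That withdrawals erode the power further. The protocol provides for withdrawals, but gives no rate and does not say whether those patients are replaced, so no loss can be calculated.

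Finally, the protocol already plans relative risks with confidence intervals and nowhere says that non-significance will be read as showing antibiotics unnecessary. That misreading is a risk to guard against and not something the plan commits to.

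**Conclusion.** The point holds in this form: the 80% power is tied to no infection rates, and it is not delivered at the only rates the protocol cites. If all arm rates lie within 5–18%, power with 36 per group is at most about 41% (Fisher), 46% (exact Pearson) or 49% (large-sample), and falls to about 10% at 10/5/5%. With equal antibiotic arms and 18% in control, the Fisher test passes 80% only when both arms are at about 1% or lower.

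This rests on equal groups of 36, on the three-group test at 0.05, and on carrying the background range over to the arms. It would be too strong to say that the design cannot have 80% power. The document does not settle the true rates, so what can be said is that the claim is unsupported and conflicts with the protocol's own figures. The test name is a separate labelling error with no effect on N.

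**What to change.** In the Sample Size Calculation:

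1. Replace the goodness-of-fit wording with the three-group (3x2) test that is planned.
2. State the assumed infection rate in each arm and its basis.
3. Restate the power of 36 per group as conditional on those rates, using one method throughout. For example, exact power at 18/5/5% is 45.5% for Pearson or 40.6% for Fisher; at 18/9/9% it is 21% or 17.5%. Do not describe 1.65% against 18% as giving 80%; that is a large-sample value, and the exact tests give 78% and 75%.

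In the analysis text, add one sentence: a non-significant result will be reported as inconclusive, with the risk difference and its 95% confidence interval (expected half-width about 12 to 16 points in the control-versus-antibiotic comparisons above).

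The cost is one rewritten paragraph and one added sentence. No extra patients are needed. The downside is a less favourable stated power.
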